4.2 Selection of study population at out-patient

4.2.1 Inclusion criteria

1. Aged 18 years or above
2. Follow-up at out-patient clinic or at the physiotherapy department of Queen Mary Hospital
3. Competent and agree to provide written informed consent

4.2.2 Exclusion criteria

1. Admitted to any hospitals in the past 14 days
2. Respiratory virus testing performed in the past 14 days
3. Antiviral against respiratory virus given within the past 14 days
4. Onset of new respiratory or non-respiratory symptoms within the past 14 days
5. Not sufficient saliva

4.3 Study enrollment procedures

Patients will be screened for eligibility by a research nurse. Reasons for ineligibility or non-participation of eligible candidates will be documented. A written informed consent will be signed by the patient.

5. STUDY PROCEDURES

5.1 Schedule of evaluations

5.1.1 Participants at the acute medical ward (in-patients)

On the day of enrollment:

- Inclusion and exclusion criteria
- Written informed consent
- Demographic information
- Questionnaire on vaccine history and symptoms
- Collection of saliva specimen

Follow-up after patient discharge

- Hospitalization data (length of stay, laboratory and radiological tests, treatment)

5.1.2 Participants at the out-patient clinic

On the day of enrollment:

- Inclusion and exclusion criteria
- Written informed consent
- Demographic information
- Questionnaire on vaccine history and symptoms
- Collection of saliva specimen

5.2 Assessment and clinical data collection

Initial symptom assessment will be performed by trained research nurses at the medical or at outpatient clinics. At the time of enrollment, the following information will be collected from the patient by the research staff using a standard questionnaire:

- Symptoms and date of symptom onset
- Prior use of oseltamivir or zanamivir within 14 days
- Prior use of antibiotics within 14 days
- Attended out-patient clinic for the same illness
- Close contacts with respiratory symptoms in the past 7 days
- Receive influenza vaccine in the past season
- Receive pneumococcal vaccine

The following data will be extracted from the clinical management system:

- Age, sex, comorbidities
- National Early Warning Score (NEWS) at A&E (20) (respiration rate, oxygen saturation, need for supplemental oxygen, temperature, systolic blood pressure, heart rate, level of consciousness)
- Time of hospital admission and discharge
- Clinical findings
 - Underlying disease

- Clinical symptoms and signs during hospitalization
- Hematological, biochemical, microbiological, immunological, and radiological investigation results on admission
- Need for supplementary oxygen, positive pressure ventilation, intubation, admission to intensive care unit, coronary care unit or high dependency unit during the hospital stay
- Final diagnosis

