3.3.2 Secondary outcome measurements

1. Length of hospital stay
2. Length of stay in general medical ward
3. Length of stay in high dependency unit
4. Length of stay in intensive care unit
5. Proportion of patients requiring oxygen supplementation
6. Proportion of patients requiring positive pressure ventilation
7. Proportion of patients requiring intubation
8. Proportion of patients admitted to intensive care unit
9. Proportion of patients admitted to coronary care unit
10. Proportion of patients admitted to high dependency unit
11. Proportion of patients who die during hospitalization
12. Initial blood test results on admission
13. Radiological investigation results
14. Microbiological investigations results

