4. SELECTION AND ENROLLMENT OF PARTICIPANTS

4.1 Selection of study population at in-patient

4.1.1. Inclusion criteria

1. Admitted to the acute medical ward of Queen Mary Hospital via the accident and emergency department
2. Aged 18 years or above
3. Hospitalized for less than 24 hours at the time of recruitment
4. Presented with exacerbation of underlying lung disease, acute coronary syndrome or stroke
5. Competent and agree to provide written informed consent

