6. STATISTICAL METHODS

6.1. Sample size

The sample size is based on the feasibility of the budget. A total of 100 hospitalized patients and 100 out-patients will be recruited.

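### The oxygen and ventilation outcomes count unchanged home support as events, because no pre-admission level is recorded

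*Combined protocol and SAP*

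**What the plan says.** Section 3.3.2 lists as secondary outcomes 5 and 6 "Proportion of patients requiring oxygen supplementation" and "Proportion of patients requiring positive pressure ventilation". It does not say whether the need must be new or above the patient's usual level.

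The data item behind both is in Section 5.2: "Need for supplementary oxygen, positive pressure ventilation, intubation, admission to intensive care unit", continuing to "coronary care unit or high dependency unit during the hospital stay". The window is therefore the whole stay, with no reference level.

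The background data in Section 5.2 include "Age, sex, comorbidities", underlying disease, and the National Early Warning Score (NEWS) at A&E. The listed NEWS components include "need for supplemental oxygen, temperature, systolic blood pressure, heart rate, level of consciousness". The enrolment questionnaire covers symptoms, earlier antivirals and antibiotics, contacts and vaccines. Neither list names oxygen or ventilatory support used at home.

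Under Section 4.1.1, in-patients qualify if they "Presented with exacerbation of underlying lung disease, acute coronary syndrome or stroke". The exclusions in Section 4.1.2 do not remove users of long-term oxygen or ventilation.

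**The concern.** Some patients with chronic lung disease can be expected to use oxygen, non-invasive ventilation (NIV) or CPAP at home. That is a clinical premise, and the documents give no prevalence. Such a patient meets outcome 5 or 6 by carrying on with the usual support in hospital. The outcome then mixes what the acute illness caused with what the patient brought to the hospital.

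The nearest baseline item does not separate the two. The NEWS oxygen component describes status on arrival, so it can be positive both for a home user and for someone newly hypoxic. The listed NEWS components include nothing on ventilation. Comorbidities and underlying disease show that lung disease is present, but not whether support was used at home or at what level.

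Two things are at stake: how the reported proportions are read, and the validity of any comparison of these outcomes by virus status.

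**Working it through.** The plan gives no event rate, home-support prevalence or virus-positive share, and Section 6.1 bases the sample size on budget: "A total of 100 hospitalized patients and 100 out-patients will be recruited". There is no planned figure to reproduce. Every rate below is an assumption, used to show direction and rough scale.

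**Notation.** h is the share of in-patients using the support at home, q the rate of new need among the others, and r the rate at which home users go above their usual level.

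- Counted under the plan: h + (1 − h)q
- New or increased need: hr + (1 − h)q
- Excess: h(1 − r)

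**Effect on the reported proportion.** Take q = r = 0.30, so that true new or increased need is 30%.

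- h = 5%: 0.05 + 0.95 × 0.30 = 33.5%
- h = 10%: 0.10 + 0.90 × 0.30 = 37%
- h = 20%: 0.20 + 0.80 × 0.30 = 44%

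At h = 10% among 100 in-patients, 37 are counted. Of the 10 home users, 3 went above their usual level and 7 did not. The excess ranges from zero (r = 1) to h itself (r = 0).

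**Virus comparison, home support equally common in both groups.** Assume new oxygen need of 50% in virus-positive and 25% in virus-negative patients, with r = q within each group, so the true risk ratio is 2.00. Power is for the two-sided Fisher's exact test at 0.05, with 100 in-patients split 30/70 or 20/80 by virus status (assumed).

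| h in both groups | Positive v negative | Difference | Ratio | Power 30/70 | Power 20/80 |
|---|---|---|---|---|---|
| 0% | 50% v 25% | 0.25 | 2.00 | 63.8% | 51.2% |
| 10% | 55% v 32.5% | 0.225 | 1.69 | 53.1% | 40.5% |
| 20% | 60% v 40% | 0.20 | 1.50 | 42.0% | 32.9% |

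For positive pressure ventilation at an assumed 10% v 4% (ratio 2.50):

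- h = 2%: 11.8% v 5.92%, ratio 1.99
- h = 5%: 14.5% v 8.8%, ratio 1.65
- h = 10%: 19% v 13.6%, ratio 1.40

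**Virus comparison, home support unequal.** Same 50% v 25%, then no true effect (25% in both groups).

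| h positive / h negative | Difference (true 0.25) | Ratio (true 2.00) | Difference (true 0) | Ratio (true 1.00) |
|---|---|---|---|---|
| 15% / 5% | 0.575 − 0.2875 = 0.2875 | 2.00 | 0.3625 − 0.2875 = 0.075 | 1.26 |
| 20% / 5% | 0.60 − 0.2875 = 0.3125 | 2.09 | 0.40 − 0.2875 = 0.1125 | 1.39 |
| 5% / 15% | 0.525 − 0.3625 = 0.1625 | 1.45 | 0.2875 − 0.3625 = −0.075 | 0.79 |

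In the first row dilution and inflation cancel on the ratio scale, while the difference is inflated. With no true effect, an association appears on both scales.

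**The case against.** **Any need is a legitimate measure.** Section 3.3.2 sets these outcomes beside lengths of stay and unit admissions, which describe care received. The protocol never calls them respiratory failure or deterioration, so a reader who infers that acute respiratory failure is overstated gives the outcome a meaning the documents do not. This stands. The narrower point survives: as collected, the proportion cannot be read as new need.

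**No virus comparison of these outcomes is specified.** By virus, Section 6.2 plans incidence, the attributable fraction, death rate and symptoms. The synopsis names Fisher's exact test but no groups. This also stands. The comparison is implied at most, so the bias matters only if it is made.

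**Entry requires an exacerbation.** A lung-disease patient admitted through A&E has already deteriorated, and a home user who needs more support is a true event under either definition. This is correct, and it is why the excess is h(1 − r) and not always h. The problem is confined to home users whose support does not rise.

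**The information may be recoverable.** Treatment and other hospitalization data are collected after discharge (Section 5.1.1), and the clinical management system may show home support. The documents do not settle this, so the claim that the groups can never be separated goes too far. What can be said is that no listed item provides for it.

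**The higher assumed shares are strained.** If lung disease made up one third of in-patients (the mix is not given), h = 20% would mean 0.20 ÷ (1/3) = 60% of them on home oxygen, and 10% would mean 30% on home ventilation. The lower values are the safer guide.

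**Conclusion.** The point holds in a limited form. Followed as written, the plan scores unchanged home oxygen or home ventilation as an event in outcomes 5 and 6, and no listed variable identifies those patients. The proportions therefore overstate new need by h(1 − r), an amount the documents do not allow anyone to estimate.

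A reader might infer that this masks a virus effect. The documents do not support a single direction. Dilution follows if home support is equally common in virus-positive and virus-negative patients. In-patients mix lung disease, acute coronary syndrome and stroke. If home support and virus detection both cluster in the lung-disease group, pooling can inflate an association or create one.

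Two of the 14 secondary outcomes are affected. The primary outcome, virus incidence, and the adjusted population attributable fraction do not use these data and are untouched. This is a modest defect of definition and data collection, worth correcting because the remedy is small.

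**What to change.** - Add one item for in-patients to the Section 5.2 list: home oxygen, NIV or CPAP before admission (yes/no, and usual level). It can be asked in the existing enrolment questionnaire, since in-patients must be competent to consent.
- In Section 3.3.2, define outcomes 5 and 6 for reporting as new need, or need above the recorded usual level. Keep any use during the stay as an additional description.
- If these outcomes are compared by virus status, name the groups in Section 6.2 and present the comparison by presenting condition (lung disease, acute coronary syndrome, stroke).

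The cost is one field and a revised definition, with no change to patient care. Slightly fewer events will be counted, and some patients will be hard to classify where the usual level is poorly recorded. With 100 in-patients, results by presenting condition will be imprecise and should be read as descriptive.

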5.3 Detection of respiratory viruses

5.3.1 Specimen collection

Patients will be asked to spit out saliva (~1 ml) into a sterile container and viral transport medium (VTM) will be added as we described previously (5, 6). The specimens will be transported to the laboratory and stored at -80°C until testing.

5.3.2 Molecular testing of respiratory virus

Saliva will be tested for respiratory viruses using a commercially available multiplex PCR panel.

6. STATISTICAL METHODS

6.1. Sample size

The sample size is based on the feasibility of the budget. A total of 100 hospitalized patients and 100 out-patients will be recruited.

6.2 Analysis of the study

Crude incidence of each respiratory virus and overall respiratory virus infection among hospitalized patients and out-patients will be estimated. To adjust for the background rate of respiratory virus detection among out-patients, we will calculate adjusted population attributable fraction (aPAF) as described previously (22). Conceptually, aPAF represents the fraction of hospitalization that can be attributed to a particular pathogen. Death rate of each detected respiratory virus and overall respiratory virus infection among patients in the acute medical wards will be estimated.

For symptomatology of respiratory viruses, frequencies and proportions of respiratory and non-respiratory symptoms for each respiratory virus and overall respiratory virus infection will be calculated.

Statistical test will be performed using SPSS version 23.0. A *P* value of <0.05 with two-sided testing will be considered statistically significant.

7. STUDY TEAM and STUDY SITE

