2. BACKGROUND AND RATIONALE

2.1. Background and study rationale

Respiratory viruses cause severe infections, and contribute to a substantial number of hospitalizations, admission to intensive care units and deaths (1). Many hospitalizations due to respiratory virus infection are related to pneumonia or exacerbation of chronic lung disease. In addition, many hospitalizations are related to extrapulmonary complications, such as acute coronary syndrome or stroke (2).

Previous studies have reported the incidence of respiratory viruses among patients with pulmonary complications (3), or the association of respiratory viruses with acute coronary syndrome or stroke (4). However, there are several problems associated with these studies. First, many of these studies are retrospective in nature, and therefore testing was only performed in selected patients with respiratory symptoms. Hence, many patients without respiratory symptoms were not recruited. Second, respiratory virus can be detected in some asymptomatic individuals. Therefore, the presence of respiratory virus may be an incidental finding rather than the cause of the complication. Third, many studies only focus on a few respiratory viruses, especially on influenza virus.

This study aims to address these issues. We propose to conduct a prospective cohort study. We will recruit hospitalized adult patients with exacerbation of underlying lung disease, acute coronary syndrome or stroke. As controls, we will recruit outpatients follow-up for chronic heart disease, chronic lung disease or neurological conditions. We will collect saliva from study participants and perform respiratory virus testing using a multiplex PCR panel. Our previous studies have shown that there is a high concordance between results from respiratory virus testing on saliva and nasopharyngeal specimens (5, 6).

Our study will provide accurate data on the epidemiology of respiratory viruses in pulmonary and extrapulmonary complications. These data are important for clinicians, public health practitioners and scientists.

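### The per-virus aPAF has no stated rule for zero positive controls: with 0/100 out-patients positive it equals the crude detection rate, which is likely for viruses with a background of about 1% or less

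*Combined protocol and SAP*

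**What the plan says.** Section 6.1 fixes the numbers: "A total of 100 hospitalized patients and 100 out-patients will be recruited". The stated basis is cost alone: "The sample size is based on the feasibility of the budget". No detection rate, power or precision target is given.

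Section 6.2 plans estimates by virus as well as overall: "Crude incidence of each respiratory virus and overall respiratory virus infection among hospitalized patients and out-patients will be estimated". The background correction is defined by citation, "we will calculate adjusted population attributable fraction (aPAF) as described previously (22", and interpreted per pathogen: "Conceptually, aPAF represents the fraction of hospitalization that can be attributed to a particular pathogen". The only inferential rule in that section is a P "value of <0.05 with two-sided testing will be considered statistically significant". The synopsis adds Fisher's exact test for categorical variables.

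The text gives no aPAF formula, covariate list, interval method, rule for zero positive controls, minimum count or pooling of rare viruses. Section 5.3.2 names neither the panel nor the number of its targets: "Saliva will be tested for respiratory viruses using a commercially available multiplex PCR panel". Section 2.1 explains why a correction is needed, noting that "respiratory virus can be detected in some asymptomatic individuals", but gives no rate.

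**The concern.** The aPAF is the study's answer to incidental detection, which Section 2.1 lists as a weakness of earlier work. The correction relies on the out-patients supplying a background rate. A multiplex panel spreads the overall background across several viruses, and Section 4.2.2 excludes out-patients with new symptoms in the previous 14 days. Both make it more likely that a given virus appears in none of the 100 controls.

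When that happens, the estimated odds ratio is infinite and the aPAF returns the uncorrected detection rate. A reader applying the plan's own interpretation would take every detection of that virus as a cause of admission, even where the data are compatible with no association. Without an interval, nothing attached to the aPAF would show this.

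**Working it through.** **Inputs.** From the documents: 100 cases and 100 controls (Section 6.1); two-sided 0.05 (Section 6.2). Assumed, because the documents are silent: per-virus background rates of 0.5% to 3%, and aPAF = p_case × (1 − 1/OR), unadjusted. Simple subtraction, p_case − p_control, is checked as an alternative. The sample size has no statistical inputs, so there is no figure of the plan to reproduce.

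**Step 1: what zero positive controls does.** With p_control = 0 the OR is infinite, so 1/OR = 0.
- Ratio form: p_case × (1 − 0) = p_case.
- Subtraction form: p_case − 0 = p_case.

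Both return the crude case rate. An ordinary maximum-likelihood fit has no finite OR, and the Wald interval does not exist.

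**Step 2: how often.** P(0 of 100 positive) = (1 − p)^100.

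| Assumed background per virus | P(0/100) |
|---|---|
| 0.5% | 0.995^100 = 0.606 |
| 1% | 0.99^100 = 0.366 |
| 2% | 0.98^100 = 0.133 |
| 3% | 0.97^100 = 0.048 |

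For all viruses combined the background must be at least as high as for any single one. At an assumed 5% overall, 0.95^100 = 0.006.

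**Step 3: false attribution.** Take a true rate of 1% in both groups, so the true aPAF is 0. The chance of zero positive controls and at least one positive case is 0.366 × (1 − 0.366) = 0.232, or 23%.

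**Step 4: what 0/100 actually shows.** The exact 95% upper limit for the background is 1 − 0.025^(1/100) = 3.6%.

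**Step 5: strength of evidence with zero positive controls.** The limits below put the lower 95% limit of the OR into the formula and hold the case rate fixed.

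| Cases v controls positive | aPAF | Fisher P | Exact OR lower limit | aPAF at that limit |
|---|---|---|---|---|
| 2 v 0 | 2.0% | 0.50 | 0.188 | 0.02 × (1 − 1/0.188) = −8.6% |
| 5 v 0 | 5.0% | 0.059 | 0.935 | 0.05 × (1 − 1/0.935) = −0.35% |
| 6 v 0 | 6.0% | 0.029 | 1.211 | 0.06 × (1 − 1/1.211) = +1.0% |

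At least 6 positive cases are therefore needed for P < 0.05.

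**Step 6: the choice of method matters.** At 5 v 0, Firth's penalised likelihood gives an OR of 11.6 and an aPAF of 0.05 × (1 − 1/11.6) = 4.6%. Its profile lower limit is OR 1.28, which gives 0.05 × (1 − 1/1.28) = +1.1%. The exact limit includes zero and the Firth limit does not.

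**The case against.** The strongest reply has four parts.

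1. **The frequency is not established.** A reader might infer that many viruses on the panel will have no positive out-patients. The documents do not support that, because they give neither background rates nor the panel's size. At 3% or more per virus, zero positive controls is unlikely. What stands is the conditional statement for viruses at about 1% or below.

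2. **Intervals do exist.** A reader might infer that no usable interval can be had. That is true only of the ordinary Wald or maximum-likelihood fit, and the plan does not even name logistic regression. Exact, profile-likelihood and penalised limits are all available. What stands is that the text chooses none, and Step 6 shows that the choice can change the conclusion.

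3. **The plan has safeguards.** Crude rates in both groups would show the 0/100, and Fisher's test, if applied to virus detection, would give P = 0.059 at 5 v 0. Reference 22 may also supply an interval or a rule for selecting pathogens. These points have weight, and it would be too strong to say that the plan must report every detection as causal. But none of this is attached to the aPAF in the text, and the stated interpretation of the aPAF carries no such caution.

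4. **The objectives concern respiratory virus infection as a whole.** Section 3.1 does not ask for individual viruses, and the any-virus aPAF is much less exposed. This stands and limits the reach of the point. The per-pathogen reading comes from Section 6.2 and the synopsis.

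**Conclusion.** The point holds for per-virus aPAFs of low-prevalence viruses. With 0/100 positive controls the background correction does nothing under either form considered, and the text has no rule or interval to prevent a reading of full attribution. At an assumed 1% background this situation has a 37% chance for each virus. With no true association, the chance of a result that reads as fully attributable is 23%.

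The arithmetic is firm. The frequency rests on assumed background rates. The aPAF formula is also assumed, since reference 22 was not available, and the lower limits shown ignore uncertainty in the case proportion. The point does not undermine the any-virus aPAF. It should be corrected, and doing so needs no additional participants.

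**What to change.** In Section 6.2:

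1. State the aPAF formula and covariates. Name the any-virus aPAF as the primary aPAF and label the per-virus aPAFs secondary.
2. Pre-specify one zero-cell method rather than a choice of methods. Exact conditional OR limits would be consistent with the planned Fisher's exact test. Report every aPAF with a 95% interval that also reflects uncertainty in the case proportion, for example by a method that combines the separate intervals. A simple bootstrap will not serve for zero cells, because resampling 0/100 always returns 0/100.
3. Below a pre-set total of positives, report counts and exact intervals in both groups and no aPAF. Fewer than 6 is a natural cut-off, since 6 is the smallest count that can reach P < 0.05 with zero positive controls. A penalised point estimate alone is not enough, because at 5 v 0 it moves only from 5.0% to 4.6%.
4. Do not describe a virus as attributable when its aPAF interval includes zero.

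The cost is a few sentences and possibly a routine outside SPSS. Intervals will be wider, and the rarest viruses will have no aPAF.
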